**Decisions about Cancer Screening in Alzheimer's Disease**  
**(DECAD)**

**PROTOCOL**  
**4.28.2022**

**BACKGROUND AND STUDY AIMS**

The incidence of both Alzheimer's disease and related dementias (AD) and of breast cancer increases with age; thus, many older women with AD are faced with questions about breast cancer screening. Having AD can impact a women's ability to participate in her medical decision-making about breast cancer screening. As a result, AD family caregivers (hereafter referred to as caregivers) are frequently involved in making decisions about mammography. Each year over 800,000 women with AD receive screening mammography. Caregivers cite decision-making and procedures related to mammograms as particularly stressful and there is a lack of data that mammography screening helps women with AD live longer or better.

The average life expectancy of older women with AD is <10 years. Current guidelines recommend not screening women with a life expectancy of <10 years. The rationale is that these women will not live long enough to experience the life prolonging benefits of mammography screening. Instead, screening these women can put them at risk for physical and psychological harm as a result of over diagnosis, overtreatment, additional tests due to false positives, and the identification of clinically unimportant cancer. Conversely, while mammography screening may not help older women with AD live longer, it may help find breast cancers earlier when they are easier to treat. Therefore, it is important that women with AD and their caregivers have information to make an informed decision about screening. The goal of our project is to test if an evidence-based decision aid for caregivers can improve the quality of decision-making about mammography in older women with AD.

A decision aid for AD caregivers about mammography could improve the quality of medical decision-making, by informing caregivers about the risks, benefits, and their choices. No decision aids exist to support AD caregivers with decisions about mammography despite the frequency that caregivers are approached with this decision. The DECAD Study will test if a decision aid can support AD caregivers and patients in making decisions about breast cancer screening by improving markers of decision quality. The study aims are:

**Primary Aim: To examine the effect of a mammography screening decision aid intervention for older women with AD on markers of decision quality among caregivers.**

Hypothesis: Caregivers of patients who receive the decision aid will have lower levels of decisional conflict (primary outcome) and higher levels of decision-making self-efficacy (secondary outcome) about breast cancer screening in older women with AD, compared to the control group.

**Secondary Aim: To examine the effect of a mammography screening decision aid intervention for caregivers on the utilization of mammograms in older women with AD.**

Hypothesis: Women with AD who are randomized to receive the decision aid will receive less mammography screening at 15 and 24 months after the intervention, compared to the control group.

**Exploratory Aim: To identify the factors that are associated with impact of a decision aid intervention on mammography screening cessation in older women with AD.**

Exploratory Hypothesis: Among the dyads randomized to receive the decision aid, caregivers of patients with more severe cognitive impairment, greater co-morbidities, or older age will experience a greater reduction in frequency of mammograms in the 15 and 24 months following the intervention.

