**Table 1. Inclusion and exclusion criteria for the DECAD Trial**

INCLUSION CRITERIA	
Patients	Caregivers
Female and 75 years or older	18 years or older
At least one mammogram in the past five years	Primary family caregiver of the patient*
Primary care visit scheduled in the next 12 months	
Diagnosis of AD as determined by ICD-10 code	Ability to provide informed consent
Ability to provide informed consent or assent	
Ability to communicate in English	Ability to communicate in English
EXCLUSION CRITERIA	
Patients	Caregivers
Permanent resident of a nursing facility	Caregiver is a non-family member who is not a legal Healthcare Power of Attorney
Had a mammogram in the past 6 months	Less than a 7 th grade education**
Primary care visit scheduled is not the first visit with the PCP	
Made a decision to stop getting mammograms	Made a decision that the patient will stop getting mammograms
History of Atypical Ductal Hyperplasia, lobular carcinoma in situ, ductal carcinoma in situ, or invasive breast cancer or other cancer in the past 5 years.	Has a diagnosis of AD or has a serious mental illness such as bipolar or schizophrenia as determined by ICD-10 code
Has mild cognitive impairment, serious mental illness such as bipolar or schizophrenia as determined by ICD-10 code	

\* Identified by the patient or listed as primary caregiver in EMR.

\*\*The reading level of the decision aid is 7th grade.

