Primary outcome	Feel Informed Values clarification	Decisional Conflict	Decision Conflict Scale	16-items on a 1-5 Likert scale. Measures uncertainty around a decision, whether	Scores range 0-100; Lower	T1 T3	Caregiver reported

				one feels informed, clear about their personal values, and supported in their decision-making.	scores indicate less conflict.		
Secondary outcomes	Belief in ability to make and participate in shared decision making	Decision-making self-efficacy	Decision Self-Efficacy Scale (DSE)	11-items on a 5-point Likert scale. Measures of self-confidence or belief in one's ability to make decisions	Low, medium, high decision self-efficacy. Scores range 0-100	T1 T3	Caregiver reported
		Receipt of screening	DECAD Created	Review primary care notes, radiology reports, and documentation on screening/preventive care; caregiver report	Yes or no determination	T4 T5	Pt EMR; Caregiver reported
	Involvement in the decision	Caregiver role in decision-making	Adapted from the Control Preferences Scale	4-items to assess preferences for and involvement in making decisions on their own or sharing responsibility with the pt or doctor.	Active vs. passive/shared with doctor (since aim of decision aids is to help dyads be more active in decision-making)	T3	Caregiver reported
		Patient role in decision-making	Adapted from the Control Preferences Scale	2-items to assess involvement in making decisions on their own or sharing responsibility with their family or doctor.	Active vs. passive/shared with doctor (since aim of decision aids is to help dyads be more active in decision-making)	T3	Patient reported
Other measures		Socio-demographics	DECAD Created	32 item questionnaire to measure items such as relationship to the patient, frequency and type of contact with the patient, geographic distance from the patient, education level, annual income, self-reported health status, etc.	Co-variates	T1	Caregiver reported
	Does severity of the patient's cog and functional impairment impact caregiver decision making	Severity of patient's cognitive impairment	Dementia Severity Rating Scale (DSRS)	12-item questionnaire for caregivers to assess severity of AD in 12 major functional and cognitive domains.	Score ranges from 0 (mild) to 54 (severe).	T1	Caregiver reported
			Caregiver Appraisal of Function and Upset (CAFU)	15-item questionnaire for caregivers to measure ADLs and iADLs impairment and how much those impairments upset or burden the caregiver		T1	Caregiver reported

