#### Step 3: Secondary Aim

- A binary indicator variable for receipt of mammograms within 15 months and within 24 months from the intervention date will be used as a secondary outcome variable.
- A logistic model with group (decision aid or control) as the independent variable will be used adjusting for recruitment sites (e.g., EH, IUH and IADC) and other potential baseline covariates found to be different in univariate comparisons.

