#### Step 4: Exploratory Aim

- Once we have tested our hypothesis for the main effects, we will also perform hypothesis-generating exploratory analyses to examine effects in sub-groups of patients and caregivers.
- Hypothesized sub-group analyses will be used for both the primary and secondary outcomes examining the moderating effect of patients' and caregivers' characteristics on decision aid impact.
- The following patient variables will be included in sub-group analyses: age, level of cognitive impairment, number of co-morbidities, and their role in mammography decisions.
- The following caregiver variables will be included in sub-group analyses: relationship to the patient, level of education, health literacy, and perceived burden of mammography for the patient and for them.
- We will include each of these variables in the ANCOVA models for the primary outcome, in the logistic models for the secondary outcome and test for interactions between these variables and intervention group adjusting for recruitment sites and other potential baseline covariates. Significant interaction between a patient/caregiver characteristic variable and group would indicate different intervention effects in the dyad subgroups defined by the variable.

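### The exploratory aim concerns cessation and frequency of mammograms, but the only utilization endpoint is a cumulative yes/no, and the hypothesis is worded for one arm while the planned test uses both (minor).

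*Combined protocol and SAP*

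**What the plan says.** The Exploratory Aim, under Background and Study Aims, is "To identify the factors that are associated with impact of a decision aid intervention on mammography screening cessation in older women with AD". Its hypothesis opens "Among the dyads randomized to receive the decision aid, caregivers of patients with more severe cognitive impairment, greater co-morbidities, or older age" and predicts that these "will experience a greater reduction in frequency of mammograms in the 15 and 24 months following the intervention". The primary and secondary hypotheses both name the control group as comparator; this one names none.

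Table 3 (Measures) scores receipt of screening as a "Yes or no determination" at T4 and T5, from the medical record and caregiver report. Step 3 of the Statistical Plan analyses "A binary indicator variable for receipt of mammograms within 15 months and within 24 months from the intervention date". No count or rate of mammograms received is defined. Prior screening enters only as eligibility: "At least one mammogram in the past five years", and none in the past six months. The one item that asks for a number of mammograms concerns how many more are expected, which is an intention.

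Step 4 adds each patient or caregiver variable to the ANCOVA and logistic models and will "test for interactions between these variables and intervention group". Patient age, cognitive impairment and number of co-morbidities are on its list. It describes these analyses as hypothesis-generating.

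**The concern.** Three statements that should describe one analysis do not. The aim and hypothesis speak of stopping and of frequency. The endpoint records only whether any mammogram occurred. The hypothesis looks inside one arm, and the analysis compares two.

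The endpoint gap is the substantive part. An aid may work by persuading a dyad to make the next mammogram the last. A cumulative indicator codes that woman Yes at 15 months and Yes at 24 months, so this way of stopping goes unrecorded although the aim is about stopping.

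The wording gap matters less. A report could describe a gradient within the decision-aid arm, or the interaction, and cite the protocol for either. Only the interaction speaks to whether the aid's effect differs between subgroups, because older or sicker women may be screened less without any aid.

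**Working it through.** **No stated figure is at issue.** The plan gives no power for the exploratory aim. Its one calculation, for decisional conflict and self-efficacy, reproduces: a two-sided t-test with 202 per group has 80.2% power at effect size 0.28 and 92.6% at 0.34, and 202/0.95 gives 213. Nothing below changes it.

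**What the endpoint can distinguish.** Applying the Step 3 definition to four histories:

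| History after the intervention | Within 15 months | Within 24 months | Count by 24 months |
|---|---|---|---|
| None | No | No | 0 |
| One at month 3, then stops | Yes | Yes | 1 |
| Months 3 and 18 | Yes | Yes | 2 |
| One at month 18 | No | Yes | 1 |

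The second and third rows are identical on the planned endpoint. The 24-month window contains the 15-month window, so a Yes can never become a No. Immediate stopping is registered (first row); stopping after one more is not.

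**Illustration of size.** All distributions here are assumptions, the comparison is of whole arms (213 each), and this is not the subgroup question. Control: 0/1/2 mammograms in 50/30/20%. Scenario A for the aid arm: 50/40/10%. Scenario B: 55/35/10%.

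- Control mean 0.30 + 2×0.20 = 0.70; variance 0.30 + 4×0.20 − 0.49 = 0.61.
- A: mean 0.60, variance 0.44. B: mean 0.55, variance 0.4475.
- Yes/no, z = difference / √(2p(1−p)/213), with p the average proportion. A: 50% v 50%, z = 0, power 5%, which is built into the scenario. B: 50% v 45%, z = 0.05/0.0484 = 1.03, power 18%.
- Count, difference in means, z = difference / √((v1+v2)/213). A: 0.10/0.0702 = 1.42, power 30%. B: 0.15/0.0705 = 2.13, power 57%.

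**Why robust standard errors.** These counts vary less than Poisson counts (0.61 against a mean of 0.70; 0.44 against 0.60), so model-based Poisson errors are too large. In A the log rate ratio is ln(0.70/0.60) = 0.154, with model-based error √(1/149.1 + 1/127.8) = 0.1205 and true error √(0.61/(213×0.49) + 0.44/(213×0.36)) = 0.1076. The test statistic then has mean 1.28 and SD 0.89, and power is about 22%. The same steps in B give about 50%. With the true errors, power returns to about 30% and 57%.

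**The subgroup question.** Suppose the aid acts in one half of the women only, with 106 per arm-by-subgroup cell, and use robust errors for the log rate.

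- A: variance 3×0.61/(106×0.49) + 0.44/(106×0.36) = 0.0468; z = 0.154/0.216 = 0.71; power about 11%.
- B: variance 3×0.61/(106×0.49) + 0.4475/(106×0.3025) = 0.0492; z = 0.241/0.222 = 1.09; power about 19%.
- Yes/no interaction on the log-odds scale. A: 5%. B: variance 3/(106×0.25) + 1/(106×0.2475) = 0.1513; z = 0.201/0.389 = 0.52; power about 8%.

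**Hypothesis against analysis.** The hypothesis restricts to one arm ("Among the dyads randomized to receive the decision aid, caregivers of patients with more severe cognitive impairment"). Step 4 fits both arms and reads a significant interaction as a different effect of the aid. That matches the aim, so the hypothesis sentence is what is out of line.

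**The case against.** The strongest reply has four parts.

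- Frequency may simply mean the proportion screened. The Statistical Plan's overview uses the word that way for categorical variables, and on that reading the yes/no endpoint compared with control is adequate. The text does not settle the meaning. This reply stands in part, but it does not help with cessation, which the aim names separately.
- The power gain is illustrated for whole arms under chosen distributions, one of which removes any yes/no signal by construction. This stands. For the interactions the aim needs, even the count has low power.
- A count may be incomplete. T5 is a record review only, recruitment includes support groups and aging-services agencies, and the protocol itself qualifies record access when it describes tracking of the index visit. This stands as a cost.
- The missing pre-enrolment frequency might be called a defect. Under a randomised comparison it is not needed, since the control arm supplies the reference. It would be needed only if a within-woman change were intended.

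A reader might infer from the hypothesis that the trial will test a gradient within the decision-aid arm, and could then declare effect modification when the aid has no effect in any subgroup. The documents do not support that. No one-arm test is specified anywhere, and Step 4 sets out the two-arm interaction for all three named characteristics.

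**Conclusion.** The concern holds as a minor one. The endpoint cannot register stopping after one further mammogram, although cessation is the stated subject of the exploratory aim; this follows from the definitions and needs no assumption. The one-arm wording disagrees with Step 4, but the planned analysis is sound and rewording changes no result.

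How much information is lost depends on how often women have exactly one further mammogram and then stop, which the documents do not give. Under the assumed distributions, yes/no has 5% and 18% power for a whole-arm difference where a count has about 30% and 57%. For an interaction the count reaches only about 11% and 19%. The primary outcome, the listed secondary outcomes and the sample size are unaffected.

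**What to change.** 1. At the T4 and T5 record reviews, record the date of each screening mammogram, kept apart from diagnostic follow-up imaging. Radiology reports are already a listed source.
2. Add, as an exploratory outcome, the number of screening mammograms through 24 months, starting from the same date as the yes/no indicator. Use a Poisson or negative binomial model with robust standard errors and an offset for observed time, and apply the Step 4 group interaction to it for cognitive impairment, co-morbidity and age.
3. Keep the yes/no indicator at 15 and 24 months as the listed secondary outcome.
4. Reword the hypothesis: the difference in screening between decision aid and control is larger in women with more severe impairment, more co-morbidity or older age, tested by the Step 4 interaction. State whether frequency means the number per woman or the proportion screened.

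The cost is protocol wording and a date field in an existing abstraction. There are two downsides. It adds one exploratory outcome with low power for interactions, to be reported with intervals and not as confirmation. Counts may also be incomplete where record access is limited, particularly after T4, so the report should give the number of women whose records were available through 24 months, by arm.

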## METHODS

### Study Design:

- Two arm, randomized controlled trial.
- 426 AD patient-informal caregiver dyads with completed baselines. 213 dyads receive the decision aid on mammography (Appendix 1 and Appendix 2) and 213 dyads to receive a control condition in the form of a two-page paper pamphlet on home safety developed by the American Geriatrics Society Foundation for Health in Aging (Appendix 3).

### Participants:

- Patients will be women, age 75 and older with a diagnosis of Alzheimer's disease or related dementia.

**Table 1. Inclusion and exclusion criteria for the DECAD Trial**

INCLUSION CRITERIA	
Patients	Caregivers
Female and 75 years or older	18 years or older
At least one mammogram in the past five years	Primary family caregiver of the patient*
Primary care visit scheduled in the next 12 months	
Diagnosis of AD as determined by ICD-10 code	Ability to provide informed consent
Ability to provide informed consent or assent	
Ability to communicate in English	Ability to communicate in English
EXCLUSION CRITERIA	
Patients	Caregivers
Permanent resident of a nursing facility	Caregiver is a non-family member who is not a legal Healthcare Power of Attorney
Had a mammogram in the past 6 months	Less than a 7 th grade education**
Primary care visit scheduled is not the first visit with the PCP	
Made a decision to stop getting mammograms	Made a decision that the patient will stop getting mammograms
History of Atypical Ductal Hyperplasia, lobular carcinoma in situ, ductal carcinoma in situ, or invasive breast cancer or other cancer in the past 5 years.	Has a diagnosis of AD or has a serious mental illness such as bipolar or schizophrenia as determined by ICD-10 code
Has mild cognitive impairment, serious mental illness such as bipolar or schizophrenia as determined by ICD-10 code	

\* Identified by the patient or listed as primary caregiver in EMR.

\*\*The reading level of the decision aid is 7th grade.

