- We will consider any woman age  $\geq 75$  years with a diagnosis of AD or related dementia who has received a mammogram in the past 5 years (but not in the past 6 months) and who does not have a history of breast cancer or documentation in her EMR that she has decided to stop mammography.
- We will approach the primary family caregiver/ informant for each eligible woman. Caregivers will be eligible if they are a caregiver for the patient and intend to accompany the patient to their next primary care visit.
- Rolling enrollment will take place over 36 months with an average monthly enrollment of 11-12 dyads.

Figure 1.

DECAD ↵

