- The 15 month follow-up (T4) will be in-person or via phone and include an assessment with the caregiver and a review of the patient's EMR. This interview may be audio recorded. In the event we have exhausted the attempts to reach the participant/caregiver by phone or in person, we will send a paper copy of a letter explaining the request to have them complete the survey on paper and return to the research assistant.
- The 24 month follow-up (T5) will include a review of the patient's EMR (only).
- See Table 3 and Figure 1 for a complete list of measures and timing of collection.

*Statistical Plan:*

Step 1: Overview

- For analysis, we will examine univariate distributions of continuous variables in order to detect any potential violations of assumptions to our planned parametric methods of analyses.
- We will transform variables as needed to ensure normal distribution assumptions are met.
- We will use nonparametric methods if transformations are inadequate.
- Demographic characteristics of the patients and caregivers will be compared between the two groups in order to evaluate if randomization is effectively balanced. We will include caregiver sex as a moderating biological variable and examine the influence of sex on caregivers' decisional conflict and other factors associated with the impact of our decision aid interaction on mammography screening use.
- We will use Chi-squared tests or Fisher's exact tests to compare the frequencies of categorical variables. Analysis of variance (ANOVA), or its nonparametric alternative, the Wilcoxon rank sum test, will be used to compare the distribution of continuous variables between the groups.
- We will use SAS 9.4 for all analyses (SAS Institute, Carey, NC).

Step 2: Primary Aim

- Analysis of covariance (ANCOVA) models will be used to compare mean Decisional Conflict Scale (DCS) scores between the intervention and control groups. For each caregiver, the difference in DCS scores from baseline to follow-up will be used as the dependent variable in the ANCOVA with randomization group assignment as the independent variable adjusting for the stratification variable of recruitment site and for other potential baseline covariates that are found to be significantly different between the two groups in univariate comparisons.

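### Time since last mammogram can range from 6 months to 5 years at entry but is not a pre-specified covariate in the receipt models, so the secondary aim may lose power that is cheap to keep

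*Combined protocol and SAP*

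**What the plan says.** **Entry.** Table 1 includes patients with "At least one mammogram in the past five years" and excludes those who "Had a mammogram in the past 6 months". Step 1: Identification of Potential Participants repeats the window: a woman "who has received a mammogram in the past 5 years (but not in the past 6 months".

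**Endpoint.** The Statistical Plan, Step 3: Secondary Aim, analyses "A binary indicator variable for receipt of mammograms within 15 months and within 24 months from the intervention date".

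**Model.** The same step fits a logistic model on group, "adjusting for recruitment sites (e.g., EH, IUH and IADC) and other potential baseline covariates found to be different in univariate comparisons".

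**Where the interval could appear but does not.**
- Randomisation (Step 2: Enrollment) is stratified by site only.
- The balance check in the Statistical Plan, Step 1: Overview, says "Demographic characteristics of the patients and caregivers will be compared between the two groups"; screening history is not mentioned.
- The patient moderators in Step 4 are age, cognitive impairment, co-morbidities and role in the decision.
- Table 3 lists no item for the date of the last mammogram. The nearest are four items on experience with mammograms.

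**Wording of the aims.** The secondary hypothesis is that the aid arm will have less screening. The exploratory aim concerns "factors that are associated with impact of a decision aid intervention on mammography screening cessation", although its hypothesis speaks of frequency of mammograms. Cessation is not defined separately from non-receipt.

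**The concern.** The window mixes women who screen regularly with women who have not been screened for years but have no recorded decision to stop. It is plausible that these groups differ in their chance of a mammogram in the next 15 or 24 months whatever the arm. If so, the interval explains part of the variation in the endpoint, and a logistic model without it has less power to show an effect of the aid. No power is stated for receipt, so there is no known margin to spend.

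The second issue is interpretation. A woman who keeps a two- or three-year rhythm may simply not fall due inside a 15-month window. Counting her as having stopped would blur the exploratory question.

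**Working it through.** **1. The plan's own figures.** STATISTICAL POWER gives 202 completing dyads per group, with 80.2% power for an effect size of 0.28 and 92.6% for 0.34. A two-sided two-sample t-test at 0.05 gives 80.16% and 92.63%, and 202/0.95 = 212.6, rounded up to 213. These reproduce, but they concern the caregiver scales. For receipt, 202 per arm has 80% power for a difference of about 11.9, 13.8 or 13.4 percentage points from an assumed control rate of 30%, 50% or 70%.

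**2. Power with and without the interval.** All rates here are assumptions. There are 202 women per arm, a conditional odds ratio of 0.55 and three interval groups (recent, middle, long ago), with shares 40/40/20% (34/33/33% in the last row). Each scenario has 2,000 simulated trials and a Wald test at 0.05. The share of outcome variance explained among controls is R² = Σw(p − p̄)² / [p̄(1 − p̄)]. For the strong row, p̄ = 0.4×0.75 + 0.4×0.45 + 0.2×0.10 = 0.50 and R² = (0.025 + 0.001 + 0.032)/0.25 = 0.232.

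| Control receipt by group | R² | Power without | Power with | Gain (points) |
|---|---|---|---|---|
| 50/50/50% | 0 | 84.4% | 84.8% | 0.4 |
| 55/50/40% (weak) | 0.012 | 84.3% | 84.7% | 0.4 |
| 60/50/20% (moderate) | 0.087 | 77.8% | 81.0% | 3.2 |
| 75/45/10% (strong) | 0.232 | 64.5% | 74.8% | 10.3 |
| 80/50/10% (very strong) | 0.331 | 54.5% | 68.3% | 13.8 |

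With no treatment effect, rejection rates were 5.2% to 6.0% without the interval and 5.0% to 5.9% with it. The simulation standard error is about √(0.05×0.95/2000) = 0.5 points.

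**3. Does the adjust-if-different rule recover the loss?** A covariate tested for imbalance at 0.05 after randomisation enters in about 5% of trials. The next runs use two groups, with last mammogram over 2 years ago against more recent; 213 per arm, odds ratio 0.55, 3,000 trials each, rates assumed:

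| Control receipt, recent vs over 2 years | Share over 2 years | Unadjusted | Step 3 rule | Pre-specified |
|---|---|---|---|---|
| 60% vs 25% | 40% | 75.7% | 76.5% | 80.9% |
| 65% vs 15% | 40% | 64.7% | 65.6% | 74.8% |
| 75% vs 10% | 40% | 47.9% | 48.3% | 69.0% |
| 65% vs 15% | 30% | 69.5% | 70.5% | 78.9% |

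The rule recovers 0.4 to 1.0 points; pre-specification recovers 5.2 to 21.1. Milder assumptions shrink the gain. With 15% of women over 2 years, power rises from 83% to 85% (60% vs 25%) or from 77% to 82% (65% vs 15%). With 40% over 2 years and 55% vs 35%, it rises from 82% to 83%.

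**4. Non-receipt among women still on their rhythm.** Take a rhythm of I months, with time since last mammogram at the index visit spread evenly from 6 to I. The share with none by month T is max[0, (I − 6 − T)/(I − 6)].
- 12-monthly: 0 at both 15 and 24 months.
- 24-monthly: (18 − 15)/18 = 16.7% at 15 months; 0 at 24.
- 36-monthly: (30 − 15)/30 = 50% at 15 months; (30 − 24)/30 = 20% at 24.

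Allowing a 3-month standard deviation in the rhythm gives 16.1% and 0.1% (24-monthly), and 49.5% and 19.2% (36-monthly). The 6-month exclusion applies at enrolment, and the index visit may be up to 12 months later. If a mammogram can fall in that gap, the 24-monthly figure at 15 months could reach 9/24 = 37.5%.

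**The case against.** **The plan does not shut the interval out.** Step 3 speaks of baseline covariates, not only demographic ones, so a marked imbalance could trigger adjustment. That stands: the interval is not pre-specified, which is different from being ignored. But a rule triggered by chance imbalance does little for precision.

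**A reader might infer bias, or that an excess of long-unscreened women in one arm will pass for an effect of the aid.** The documents do not support that. Allocation is randomised 1:1, and type I error stays near 5% with or without the covariate. In the two-group null runs (40% over 2 years), the Step 3 rule gave 3.8% and 3.4%. A conditional remark does hold: with 213 per arm, the arm difference in that share has standard error √(2×0.4×0.6/213) = 4.7 points, so an excess above 5 points in the aid arm occurs in about 14–15% of trials. Among those, under the null, the unadjusted test favours the aid 7–11% of the time against a nominal 2.5%. Opposite imbalances offset this over all randomisations. It is a reason to adjust, not evidence of bias.

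**The size is assumed.** The documents give no receipt rate, effect on receipt or distribution of intervals, and nothing shows that the interval is the strongest predictor. This stands; the gain may be near zero.

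**Cessation is a side issue.** The secondary hypothesis and endpoint concern receipt. Table 1 excludes women and caregivers who have decided to stop, and Table 3 collects screening intention and the expected number of further mammograms. A reader might infer that the secondary aim mislabels non-receipt as cessation; it does not. The risk lies in the exploratory aim, mainly at 15 months.

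**The date may not be in hand.** Table 1 can be applied with two yes/no answers, and some participants come from non-clinical sources. This stands, so the fix is not wholly free.

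**Conclusion.** The concern holds as a matter of power in one secondary analysis. Entry spans 6 to 60 months since the last mammogram, and the receipt models do not commit to using that interval. The loss is about 0 points of power if the interval barely predicts receipt, about 3 to 5 if moderately, and about 10 to 14 or more if strongly. The largest gain, 21 points, needs an extreme 75% vs 10% split. These figures rest on assumed receipt rates, group shares and an odds ratio of 0.55. Validity of the test is not in question.

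Separately, non-receipt is a poor stand-in for cessation at 15 months. Among women who keep their rhythm, it ranges from 0% (12-monthly) to about 50% (36-monthly); by 24 months only rhythms longer than two years, or irregular ones, are materially affected.

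The primary outcome and the 426-dyad sample size rest on the caregiver scales and do not change. The amendment is worth making because it costs little even if the interval proves a weak predictor.

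**What to change.** 1. **Data.** Record the date, or best-known month, of the last mammogram during the eligibility check. Use the last one before randomisation, so that a later mammogram, which the mailed aid could influence, does not reset the interval.
2. **Statistical Plan, Step 3.** Name time from that mammogram to the index visit as a fixed covariate in both the 15- and 24-month models, whether or not the arms differ on it. Enter it flexibly: continuous with a non-linear term, or in three or more categories. A single cut at 24 months fits screening rhythm badly. A 24-monthly screener seen at 7 months is not due until month 17, whereas one seen at 25 months is already due.
3. **Reporting.** Give a standardised risk difference beside the odds ratio, since the adjusted odds ratio is conditional on the covariates.
4. **Statistical Plan, Step 4.** Add the interval to the patient moderators and describe the endpoint as non-receipt, especially at 15 months. If cessation is to be claimed, define it separately, for example with the intention items in Table 3.

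**Cost.** SAP wording and one more item to abstract, with some imprecise dates for participants from non-clinical sources. No extra participants are needed.
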